What may be more helpful to these patients is a resource that is more convenient, less costly, and yet effective in alleviating the types of memory difficulties oftentimes seen after SAH. Online-based cognitive interventions may represent one such option. Online cognitive interventions are becoming increasingly available and offer easier access, easier delivery, and the ability to track and analyze performance on these exercises in an automated fashion. Administering exercises using paper and face-to-face encounters requires significant time and effort to deliver. *Lumosity*, one such program, claims to bolster cognitive performance by regular engagement in various games and mental exercises. It has been studied in patients with cancer related and traumatic brain injury patients. Significant improvements in processing speeds, mental flexibility and memory have been reported. No similar interventions have been reported in patients within the first few months after an aneurysmal SAH. Given the unique characteristics of many patients who survive a ruptured brain aneurysm, and the feasibility of using online cognitive interventions, we sought to evaluate its effect through a clinical randomized control study.

Study Plan:

Our study aims to determine if periodic online cognitive exercises improve memory function in ruptured cerebral aneurysm patients with disabling baseline memory deficits within the first 12 months. Eligible subjects will be physically independent but have a self-reported disabling memory deficit within the first year of their ruptured cerebral aneurysm. Screening will be determined by a series of questions either in person or over the telephone. All enrolled subjects will complete memory assessments to determine baseline function.

Assessments:

Redcap administered assessments:

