To determine the extent by which these problems affect daily life for the individual, we are including the Activity of Daily Living (ADL) questionnaire. This survey assesses standard areas of daily living to determine the number as well as the severity of the problem. This survey was designed such that patients with cognitive decline could still yield meaningful responses. This test determined normative values based on comparing a patient's baseline status to their overall score on the survey, which allows it to be sensitive to mild decline as well as severe decline in cognitive function. The test is scored by taking the total score of a patient and dividing by the number of items rated which allows the test to only measure deficits seen with activities that the patient regularly participates in. This test has a validated cut off points for determine positive results: 0-33% may indicate some impairment, 34-66% moderate impairment, 67+%: severe impairment.

Lumosity administered assessments:

1. Arithmetic Reasoning
2. Forward Memory Span
3. Reverse Memory Span
4. Digit Symbol Coding
5. Divided Visual Attention
6. Trail Making A
7. Trail Making B
8. Progressive Matrices

Then, randomization will occur to a treatment group, which will include online access to structure-oriented activities(Lumosity), and an active control group(online crosswords).

Intervention group: Participants assigned to the intervention/experimental group will undergo twenty training sessions over 10 weeks. In each session, they practice video games selected from Lumosity(<http://www.lumosity.com>), a web-based cognitive training platform that includes games designed with the purpose of improving the user's cognitive abilities (Stenberg et al., 2013). Games will be customized using an automated algorithm supplied by Lumosity, to determine performance in the various targeted skills, which include: task switching, logical reasoning, quantitative reasoning, response inhibition, numerical calculation, working memory, face-name recall, selective attention, spatial recall, spatial orientations, planning, and divided attention.

Game Name	Targeted Skill
Brain Shift	Task Switching
Brain Shift Overdrive	Task Switching
By the Rules	Logical Reasoning
Chalkboard Challenge	Quantitative Reasoning
Color Match	Response Inhibition
Disconnection	Task Switching
Disillusion	Task Switching
Division Storm	Numerical Calculation
Ebb and Flow	Task Switching
Face Memory Workout	Working Memory

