Familiar Faces	Face-Name Recall
Follow that Frog	Working Memory
Lost in Migration	Selective Attention
Memory Lane	Working Memory
Memory Match	Working Memory
Memory Match Overdrive	Working Memory
Memory Matrix	Spatial Recall
Moneycomb	Spatial Recall
Monster Garden	Working Memory
Pet Detective	Planning
Pinball Recall	Working Memory
Playing Koi	Divided Attention
Raindrops	Numerical Calculation
Rhyme Workout	Working Memory

River Ranger	Information Processing
Rotation Matrix	Working Memory
Route to Sprout	Planning
Star Search	Selective Attention
Tidal Treasures	Working Memory
Train of Thought	Divided Attention
Trouble Brewing	Divided Attention
Word Sort	Logical Reasoning

Lumosity has the ability to customize games based on the performance in five different cognitive domains. Based on the participants' performance on exercises testing speed, memory, attention, flexibility and problem solving, certain online games can be emphasized based on the needs of the patient. Of interest will also be the profile of cognitive deficits determined by the Lumosity screening process that may characterize the cognitive problems typically seen in patients with ruptured cerebral aneurysms. Based on prior literature, we will be focusing on games designed to improve divided attention, flexibility, problem solving and memory

The recommended interaction would be 2 hours per week for 10 weeks for a total training time of 20 hours over the course of the study.

Active control group: The attention control group uses a computerized crossword puzzle game. This game offers a choice between three puzzle sizes, three levels of complexity, and varying font sizes. It also includes optional help features such as filling in an unknown letter or word. There is, however, no progressive challenge to the user by either increased speed, visual field size, number of distractors, or degree of difficulty of target stimulus differentiation. Thus, the crossword puzzle program provides an appropriate, computerized attention control alternative to the active visual speed of processing training.

To facilitate rapid recruitment into the study, randomization stratification will not be performed. After 10 weeks, both groups will complete the assessments that were used at enrollment.

Research Methods and Procedures for Post SAH Memory Study

Recruitment and Screening:

Recruitment: Study participants will be recruited in the following ways:

- A. *Neurosurgery Clinic Setting:*

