 1. Study staff will be utilizing REDCap’s randomization tool. The randomization tool has been formatted to randomize patients into one of two groups, “Lumosity” or “active control”. **Stratification factors will include age (<50, 50 or older), gender, level of education (greater than high school education or not) and time since rupture of the aneurysm (<6 months or 6-12 months).** Randomization by the study staff will occur when the participant completes the demographic survey. This tool will help the study better implement a defined randomization model and allow the study staff to randomize participants easily.

[figure not shown]
Screen shots of the Project’s Randomization Tool:

b. Delivery of patient surveys

1. Surveys (CLCE-24, Working Memory, and Activities of Daily Living ADL Scale) will be sent to participants via the REDCap system. Study participants will be able to complete all surveys and submit them online. Individual emails are sent out to each person in the study. The email will contain brief instructions about completing the survey and a secured link to their individual survey queue.

Screen shot of the Survey Queue:

c. Collection of Survey Responses:

1. The REDCap database will alert the study team on which surveys were and were not completed by specific participants. The study staff will be able to send reminders to those who have not yet completed all the required surveys in their queue.

Screen shot of the participant list:

Participant List belonging to [Initial survey] "Information about you" Remove all participants

Displaying 1 - 7 of 7 Add participants Compose Survey Invitations Export list

Email	Participant Identifier	Responded?	Invitation Scheduled?	Invitation Sent?	Link	Survey Access Code	Survey Queue
[No email listed]	Disabled		-				remove
[No email listed]	Disabled		-				remove
[No email listed]	Disabled		-				remove
[No email listed]	Disabled		-				remove
[contact]	Disabled		-		-	-	
[contact]	Disabled		-				remove
[contact]	Disabled		-		-	-	

d. Data Export

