 Those with a modified Rankin 0 or 1
 Baseline memory problem affecting daily life
 Home computer or tablet with internet access

Exclusion

Unable to read or speak English

Data Analysis:

Data will be analyzed by a Spearman rank-order correlation. Data will be compared by using the number of completed puzzles and the amount of time spent completing them with changes noted on the CLCE-24 and working memory questionnaires. The Spearman rank-order will be used to show a monotonic relationship with completing strategy orientated puzzle and reduction in memory symptoms.

Table of Expected Results

Testing	Baseline	Post Intervention	Controls
CLCE-24	Cognitive and Emotional complaints: 3.3	Cognitive and emotional complaints: 1	Cognitive and emotional complaints: 3
ADLQ	Total: 17/84 or 20%	Total: 10/84 or 11%	Total: 18/84 or 21%
Working Memory	Total: 34.5 Storage: 11 Attention: 14 Executive Function: 9	Total: 20 Storage: 6 Attention: 8 Executive Function: 6	Total: 32 Storage: 10 Attention: 14 Executive Function: 8

Estimated sample size: 108 subjects total.

For CLCE-24, a sample size of 50 patients per group (total of 100 patients) can provide 80% power to detect a difference of 2 in number of complaints between the two groups, with a significance level of 0.5 and using a two-sample t-test (two-sided). For the Working memory questionnaire, a sample size of 54 patients per group (total of 108 patients) will achieve 80% power to detect a difference of 12 points between the two groups, with a significance level of 0.5 and using a two-sample t-test (two-sided).

Data Collection:

Data will be collected at different time points in this study. Please refer to table 1 for further reference.

Week 1: Consent, enrollment, completion of three Redcap assessments and Lumosity assessments. Randomization. Intervention group will receive access to Lumosity and control will get access to crossword puzzles.

Weeks 2-9: Intervention group will be reminded to complete Lumosity games; active controls will be reminded to complete cross-word puzzles

Week 10: All subjects complete the three Redcap assessments, the Lumosity assessments. Study completed at this time.

Table 1.

Group	Week 1	Weeks 2-9	Week 10
Intervention			
CLCE24/Working memory/ADLs/Lumosity	X		x
Lumosity	x	x	X
Control			
CLCE24/Working memory/ADLs/Lumosity	X		X
Active control		x	X

*At 70 day assessment, patients will have a +/-10 day window to submit questionnaires.

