Data Analysis: The primary analysis should be comparisons between the two groups for the outcome measures. T test or Mann-Whitney test can be used for comparisons and regression analysis may be performed with adjustment of baseline characteristics.

Questionnaires

For the CLCE-24, Working Memory and Activities of Daily Living Questionnaire, please see Appendix A.

Processes and controls to ensure study integrity

A key differentiator in this study is the use of online consent, data acquisition and data analysis. A concern for data being collected in this fashion concerns sampling bias and construct validity. One might think that support groups and online social networks may not capture data from patients who are older and not as familiar with technology. However, as social media improves its user interface, greater numbers of older users are being engaged. We believe *Lumosity* represents one such solution to address this concern. With regard to construct validity, we have included a series of questions we will administer over the phone in the event subjects are not actual patients of our practice for whom we have been able to review the relevant history, physical examination and imaging findings. Users of targeted social network groups are likely to be a self-selected motivated group of individuals. The likelihood that individuals without a diagnosis of brain aneurysm would be a part of this targeted social network and participate in the study seems unlikely. We hope that the relatively larger size of the dataset relative to previously published single-center series can overcome the effect any erroneous outliers may have on biasing the data.

Suitability of investigator(s) and institution

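### The plan says both that randomisation is unstratified and that it is stratified on four factors, and it leaves the primary test and its covariates open

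*Combined protocol and SAP*

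**What the plan says.** On allocation, the last paragraph of the Active control group text in the Study Plan reads "To facilitate rapid recruitment into the study, randomization stratification will not be performed". Under Data Collection Methods, Participant Randomization, the plan reads "Stratification factors will include age (<50, 50 or older), gender, level of education (greater than high school education or not", and the sentence goes on to a fourth factor, time since rupture split at 6 months. Nothing in the supplied text marks either statement as superseded.

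On analysis, the second Data Analysis paragraph (after Table 1) says "The primary analysis should be comparisons between the two groups for the outcome measures" and continues "T test or Mann-Whitney test can be used for comparisons and regression analysis may be performed with adjustment of baseline characteristics". It gives no rule for choosing between the tests, names no covariate and does not mention the four factors. A two-sided two-sample t-test is named under Estimated sample size, for sizing only. The first Data Analysis paragraph describes a Spearman correlation of puzzle use with change in score.

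On timing, the Study Plan says "All enrolled subjects will complete memory assessments to determine baseline function", and after the assessment list, "Then, randomization will occur to a treatment group". The Data Collection schedule gives the same order: "Week 1: Consent, enrollment, completion of three Redcap assessments and Lumosity assessments. Randomization". Participant Randomization sets a different trigger: "Randomization by the study staff will occur when the participant completes the demographic survey".

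**The concern.** The correct analysis depends partly on how participants were allocated. If the four factors are used to randomise and they predict outcome, an unadjusted t-test overstates its standard error: it rejects too rarely under the null and gives up power. If allocation is unstratified, the same t-test is valid and adjustment only adds precision. With two incompatible statements, a reader cannot tell which case applies.

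The open choice of test matters under either scheme. A t-test, a Mann-Whitney test and one or more adjusted regressions are all permitted. An analyst who sees the results first can report whichever is most favourable, and the nominal 5% then no longer describes the procedure.

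**Working it through.** **Inputs from the plan.** N = 108, 54 per group, difference 12 points, 80% power, two-sided t-test (Estimated sample size); SD 22.1 for brain-injured respondents (Assessments, Working memory).

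**The plan's own figure.** n per group = 2(1.960 + 0.842)² × (22.1/12)² = 15.70 × 3.392 = 53.2, rounded up to 54. Exact t power at 54 per group is 79.8%. This reproduces the plan only at a two-sided level of 0.05. The printed 0.5 would need about 15 to 16 per group, so 0.05 is used below.

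**Strata.** 2 × 2 × 2 × 2 = 16 cells; 108/16 = 6.75 per cell.

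**Closed-form check, stratified and perfectly balanced.** If the factors explain a share R² of outcome variance, the unadjusted t-test has true level 2[1 − Φ(1.96/√(1 − R²))].
- R² = 0.10: 1.96/0.949 = 2.066, giving 3.9%.
- R² = 0.30: 1.96/0.837 = 2.343, giving 1.9%.

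**Simulation.** None of the following is in the plan; all are assumed:
- four independent 50:50 factors, equally prognostic, with total R² as shown;
- a baseline score with the same factor effects and correlation r with the week-10 score given the factors;
- permuted blocks of 4 within strata, or unstratified 54:54;
- 108 complete cases and normal scores.

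There were 10,000 trials per setting, pooled to 40,000 where r does not enter. In the table, smallest p means the smallest of t-test, Mann-Whitney and four-factor regression.

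| R² of the four factors | 0 | 0.05 | 0.10 | 0.20 | 0.30 |
|---|---|---|---|---|---|
| Type I error %, fixed t-test, stratified | 5.0 | 4.7 | 4.1 | 3.2 | 2.2 |
| Type I error %, smallest p, stratified | 6.2 | 6.1 | 5.9 | 5.7 | 5.3 |
| Type I error %, smallest p, unstratified | 6.7 | 7.0 | 7.5 | 8.0 | 8.6 |
| Power %, t-test, stratified | 79.9 | 80.3 | 80.9 | 82.2 | 83.5 |
| Power %, four-factor model, stratified | 79.7 | 81.6 | 83.7 | 87.8 | 91.6 |

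- **Fixed t-test, unstratified:** type I error 4.8 to 5.2%.
- **Power forgone by the t-test, stratified:** at R² = 0.30, 91.6 − 83.5 = 8.1 points.
- **Baseline-adjusted regression also among the choices (r = 0.5):** smallest-p type I error 7.5 to 8.2% stratified, 8.8 to 10.8% unstratified.
- **Repeat simulation:** the stratified t-test at R² = 0.30 came out at 2.4%, and the unstratified smallest-p figure started at 6.6%.
- **Blocks of 12 instead of 4, R² = 0, 0.10, 0.30:** smallest p 6.3, 6.8, 6.3%; fixed t-test 4.9, 4.6, 3.0%.

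**A single prespecified linear model** (group, baseline score, four factors):
- Type I error is 4.6 to 5.5% across 40 settings.
- Power at R² = 0 and r = 0, 0.3, 0.5, 0.7 is 79, 83, 89, 97% stratified and 78, 81, 88, 97% unstratified, against about 80% for the t-test.
- Unstratified, at r = 0.5 and R² = 0, dropping the four factors and keeping baseline gives 89.3% against 88.1%.

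**Skewed scores** (gamma, mean 34.5, SD 22.1, stratified, R² = 0). For a pure 12-point shift, model v Mann-Whitney power is 88.3 v 88.6% at r = 0.5, 83.8 v 89.4% at r = 0.3 and 78.8 v 89.4% at r = 0. For a proportional fall in the mean from 34.5 to 22.5 at r = 0.5, it is 97.1 v 88.8%.

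**The case against.** The stratification conflict may be only editorial. The section naming the factors describes a randomisation tool that is already set up, so the contrary sentence may be a leftover. That is plausible, but nothing supplied confirms it. The tool's screenshot is not shown in the text under review, so no point is made about block size.

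The sample-size paragraph names a t-test, which is a natural default. It does not bind the analysis, because the later paragraph reopens the choice.

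The inflation figures are worst cases. A reader might infer that the planned analysis runs above 5%. The documents do not support that: they do not say the smallest p will be reported. Under stratification, choosing only between the t-test and Mann-Whitney gave 4.9% at R² = 0.10 and 2.9% at R² = 0.30. The plan also reports no significant CLCE-24 differences by age, gender or education, which points to a low R² for that outcome. This objection stands and limits the size of the point.

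The choice of a linear model is partly preference. With right-skewed scores, a pure shift and a weak baseline correlation, Mann-Whitney is more powerful. This also stands.

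Finally, no primary outcome is named. Three independent questionnaire tests at 5% would give 1 − 0.95³ = 14.3% familywise error, and less if the scores are correlated. That can exceed the inflation considered here, and fixing the model does not remove it.

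**Conclusion.** The point holds in two parts. The two statements on stratification contradict each other and must be reconciled. The primary analysis is neither fixed nor tied to the allocation scheme. Both should be corrected before data are examined.

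The size rests on assumed R², r and block size, and on the Working Memory score with complete data at a two-sided 0.05. With stratified allocation and prognostic factors, the unadjusted t-test runs at about 4% (R² = 0.10) to 2.2 to 2.4% (R² = 0.30) and forgoes up to about 8 points of power. With unstratified allocation it is valid. Worst-case selection among three analyses gives about 5.3 to 6.2% stratified (blocks of 4) and 6.6 to 8.6% unstratified, or about 7.5 to 11% with baseline-adjusted regression added.

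Two stronger readings are not supported. One is that the t-test is invalid: its error is in the conservative direction, and only if allocation is stratified on prognostic factors. The other is that the four factors belong in the model regardless: if allocation is unstratified, they have no design basis. CLCE-24 and ADL were not simulated. Confidence is high on the textual conflict and lower on the magnitudes.

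**What to change.** 1. Confirm which scheme REDCap runs, and correct either the Active control group sentence or the Participant Randomization sentence.
2. In the second Data Analysis paragraph, replace the open choice with one primary analysis of the group comparison: a linear model of the week-10 score on group and the baseline score of the same measure. Add age, gender, education and time since rupture as main effects only if they are used to randomise.
3. Make baseline adjustment conditional on the week-1 questionnaires being completed before allocation. The Study Plan and the Data Collection schedule imply this, but the demographic-survey trigger does not guarantee it. If the order cannot be confirmed, the baseline score should leave the model, and its power gain goes with it.
4. Keep Mann-Whitney as a sensitivity analysis and state that the Spearman correlation is not primary.

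**Gain:** type I error of about 5% per outcome, and power of about 88 to 89% against 80% at r = 0.5, with N unchanged.

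**Cost:** one corrected sentence and one replaced sentence, with no new visits, assessments or participants. The sponsor should also check that the demographic survey records all four factors. If nothing is prognostic, the loss is up to about 2 points of power: 79.2 v 80.0% stratified, and 78.0 v 79.9% unstratified when the four factors are kept. If scores are right-skewed and the effect is a pure shift, the model matches Mann-Whitney only at about r = 0.5 and is about 6 to 11 points lower at r = 0.3 to 0. Naming a primary outcome and handling multiplicity across the questionnaires must be dealt with separately.

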 - a. Patients with ruptured aneurysms that will be coming in for follow up at Rush's Neurosurgery Clinic Office can be recruited for the study. If a patient is deemed a good candidate for the study by [name] or [name], they will discuss the study with the patient at the end of their clinic visit. If the patient is willing to participate, they may be consented. After agreeing, patients will be sent an email with a secured link via REDCap to fill out a demographics survey.
- B. *Email and Phone Screen Setting:*
 - a. [name] has composed a recruitment letter to patients that can be emailed. With that letter, patients will receive contact information of who to call if interested in the study. The contact will be the Neurosurgery Department's research coordinator [name]. It will be the coordinator's responsibility to screen these potential participants over the phone. At

[figure not shown]
this point, if the patient qualifies and agrees to the study, a telephone script of the consent will be read to the patients. After agreeing, patients will be sent an email with a secured link via REDCap to fill out a demographics survey.

- C. Social Media
 - a. Via the Brain Aneurysm Foundation or the Joe Niekro Foundation
 - i. Survivors who meet the inclusion criteria via a telephone interview, will be enrolled in the study.
- D. Support Group Setting at Rush University Medical Center:
 - a. Patients with ruptured aneurysms that attend a Rush initiated monthly support group will be recruited for this study. Recruitment scripts will be provided to the facilitator of the group. If patients are interested in participating, they will be able to speak with Investigator [name] and sign a consent form after the monthly meeting. Both the facilitator and Investigators will make it very clear in their scripts that participation in the study is voluntary and not necessary to do as part of the support group meetings.

Data Collection Methods:

- A. REDCap is a secure web application that is used for building and managing online surveys and databases. The REDCap Consortium is composed of 1,308 active institutional partners in 88 countries who utilize and support the system. REDCap will be used for the following in this proposed study:
 - a. *Participant Randomization*

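### The REDCap text triggers randomisation on the demographic survey, against the plan's own baseline-first order, and nothing makes submitted baselines a condition for randomising

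*Combined protocol and SAP*

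**What the plan says.** Two parts of the plan put the baseline first.

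- **Study Plan and Assessments.** "All enrolled subjects will complete memory assessments to determine baseline function". The REDCap and Lumosity instruments are listed next, and the text continues: "Then, randomization will occur to a treatment group".
- **Data Collection, Week 1.** "Week 1: Consent, enrollment, completion of three Redcap assessments and Lumosity assessments. Randomization". Access comes after that: "Intervention group will receive access to Lumosity and control will get access to crossword puzzles".

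The operating instruction under Data Collection Methods, item A.a (Participant Randomization), names a different event: "Randomization by the study staff will occur when the participant completes the demographic survey".

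Under Recruitment, routes A (clinic) and B (email and phone) say when that survey is sent: "After agreeing, patients will be sent an email with a secured link via REDCap to fill out a demographics survey".

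Items A.b and A.c deal with the CLCE-24, Working Memory and ADL questionnaires as separate submissions in a survey queue. For incomplete ones, "The study staff will be able to send reminders to those who have not yet completed all the required surveys in their queue".

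**The concern.** Item A.a is the only text that tells staff when to use the randomisation tool. Its trigger is a survey sent at the point of agreement, not the outcome questionnaires or the Lumosity tests. A coordinator who follows it to the letter may randomise someone whose baseline is still outstanding.

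The three questionnaires are self-reported, and participants can see whether they have been given Lumosity or crosswords. A baseline answered after that may be coloured by the allocation. The Lumosity tests are exposed in another way: training and testing share a platform, so by inference a participant in that arm could train before being tested at baseline. A baseline collected in the wrong order cannot be collected again.

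Three analyses could be affected: a change-score version of the primary group comparison; the optional regression, if the baseline score is among the adjusters; and the Spearman analysis of questionnaire changes, if the arms are pooled.

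**Working it through.** **1. The passages side by side**

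| Place | Order or trigger |
|---|---|
| Study Plan / Assessments | Baseline assessments, then randomisation |
| Data Collection, Week 1 | Consent, REDCap and Lumosity assessments, randomisation, programme access |
| Recruitment, routes A and B | Agreement, then demographic survey |
| Data Collection Methods, A.a | Demographic survey completed, then randomisation |
| Data Collection Methods, A.b–A.c | Questionnaires queued separately; alerts and reminders for those outstanding |

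The first two rows agree with each other. The fourth does not require what they require. The participant list is headed "Participant List belonging to [Initial survey" and names a form titled as information about the participant. By inference this is the demographic survey, so it comes before the questionnaires. None of the available text holds back randomisation until baselines are in.

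**2. Which analyses use the baseline**

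The second Data Analysis section makes a between-group t test or Mann-Whitney test primary, without saying whether week-10 scores or changes are compared. The expected-results table gives Working Memory totals of 32 (controls) and 20 (post intervention). The difference is 12, the sample-size target, so a week-10 comparison fits the sizing. That comparison does not use the baseline.

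**3. Size, as an illustration only**

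Inputs from the documents: n = 54 per arm (sample-size paragraph) and Working Memory SD 22.1 for brain-injured patients (instrument description).

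Assumed inputs:
- two-sided level 0.05
- true effect zero
- baseline to week-10 correlation r
- a share f of one arm with a late baseline, each such baseline shifted by s points

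The level is assumed because the document prints 0.5. The plan's own figure supports 0.05: the standard error is 22.1 × √(2/54) = 4.25, the noncentrality is 12/4.25 = 2.82, and the t-test power is 0.798, which matches the stated 80%. A level of 0.5 would give power of about 0.98.

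Formulas:
- Change score: bias f·s; SD 22.1·√(2(1−r)).
- ANCOVA: bias r·f·s; residual SD 22.1·√(1−r²).
- The affected arm's variance also gains f(1−f)s², multiplied by r² for ANCOVA.
- Rejection rate: noncentral t with 106 degrees of freedom.

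Worked case, r = 0.5, f = 0.25, s = 5, change score: bias 1.25; SD 22.1; added variance 0.25 × 0.75 × 25 = 4.69; standard error √((2 × 22.1² + 4.69)/54) = 4.26; noncentrality 0.293; rejection 0.0597.

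Type I error at r = 0.5, for s = 3 to s = 5:

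| Share of one arm affected | Change score | ANCOVA |
|---|---|---|
| 10% | 5.1–5.2% | 5.0–5.1% |
| 25% | 5.4–6.0% | 5.1–5.3% |
| 50% | 6.4–8.9% | 5.5–6.3% |
| 100% (extreme) | 10.8–21.4% | 6.9–10.3% |

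For r from 0.3 to 0.7, the 25% row spans 5.3–6.6% (change score) and 5.0–5.9% (ANCOVA). At r = 0.5, a 10% error rate for the change score needs an arm-mean shift of 2.80 points; with a quarter of the arm affected, that is 2.80/0.25 = 11.2 points each. The week-10 comparison stays at 5% throughout.

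**The case against.** The strongest reply is that the sentence in A.a states a necessary condition, not a sufficient one. It follows directly on the list of stratification factors, which the demographic survey presumably supplies, and items a to d describe what REDCap does and are not a timeline. On that reading every section agrees. The reminders may concern week 10, and a questionnaire completed after the demographic survey can still precede allocation. The text does not say when the arm is disclosed, and the Week 1 schedule places access last. Harm then requires several steps: staff overlooking the stated order, participants learning their arm early, answers shifting differently by arm, and an analysis that uses the baseline.

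Much of this stands. The reading is possible, the intended order is clear, equal shifts in equal shares of both arms would cancel in the group comparison, and the illustrated effect is small unless many are affected. Part of the document and the screenshots of the randomisation tool and survey queue were not available, and they might show a hold on randomisation.

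The reply does not remove the discrepancy. The sentence says randomisation will happen when the survey is completed, not that it may not happen before. Nothing in the available text adds the missing condition, and the primary analysis is not fixed firmly enough to guarantee that the baseline stays out of it. Equal exposure of the arms cannot be taken for granted either: Table 1, if correctly extracted, marks programme use in Week 1 for the Lumosity arm but not for control.

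**Conclusion.** The concern holds. The operating trigger disagrees with the order set in the Study Plan and the Week 1 schedule, and no available text requires submitted baselines at the point of randomising. Confidence is high on the textual conflict.

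The size of any bias is unknown. It depends on how many participants are taken out of order, how far their answers shift and whether the arms differ. Under the assumptions shown it is slight at 10% to 25% of one arm and material only when about half or more is affected. This should be fixed because the step is irreversible and the correction is cheap; the numbers alone would not make it urgent.

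**What to change.** Replace the trigger sentence in Data Collection Methods, A.a, with:

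> Staff will randomise a participant only after the demographic survey, all three REDCap questionnaires and the baseline Lumosity tests have been submitted. The arm and programme access will be released only after that.

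For the questionnaires, staff can rely on the REDCap completion alert described in A.c. The Lumosity tests are not among the surveys sent through REDCap, so they need their own check before staff randomise. Comparing survey timestamps with the randomisation time at analysis is an optional safeguard.

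The cost is one sentence, one check and a short delay before allocation. The demographic survey can still supply the stratification factors. The end of the Study Plan says there will be no stratification, which conflicts with A.a. That is a separate point to reconcile, and this change works either way.
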